Dental anxiety is linked to avoidance behavior and an increased pain response during dental procedures.^{1,2} At this time, limited methods for non-pharmacological anxiety control exist. The burden of sedation dentistry comes with many risks and financial costs. Some serious unwanted side effects include compromise to the patient's respiratory drive, airway reflexes and airway patency, as well as the cardiovascular system.³ Sedation for anxiety control is also costly for the patient and healthcare system, with deleterious effects on access to care. **Dentistry is in need of anxiety control measures other than pharmacological sedation** to reduce the risk to patients, lower the cost of treatment and thus increase access to dental care. One promising approach is animal-assisted therapy (AAT) using a well-trained therapy dog. In medical settings, AAT has been implemented in various clinical situations and has been shown to help reduce pain and stress indicators in patients.⁴ Research into AAT as a non-pharmacological behavior management and anxiety reduction techniques in dentistry is limited as many publications are surveys⁵ with a low sample size and are not conducted in the pediatric and/or dental patient population.²

To explore the effectiveness of non-pharmacological anxiety-reduction approaches, we will study the effects of animal-assisted therapy (AAT) on pediatric patients undergoing invasive dental procedures that include an injection. The University of North Carolina has a unique opportunity to explore animal-assisted therapy because the dental school has a certified therapy dog. Our central hypothesis is that children who interact with a therapy dog before their dental procedure will have significantly lower physiologic and subjective responses to stress. We will test this hypothesis by following aims:

Primary Aim: We will measure the effects of animal assisted therapy on pediatric patients' stress levels by analyzing objective physiologic measures (salivary amylase and cortisol) during invasive dental procedures.

Supplemental Aims: We will measure participants' heart rate throughout dental visit, will evaluate patients' perceptions of pain and anxiety using pre-, intra-, and post-procedural surveys to assess the patients' subjective responses to animal-assisted therapy and will analyze participants' behaviors using observational coding.

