Dentistry is in need of anxiety control measures other than sedation in order to reduce risk to patients, lower the cost of treatment and increase access to dental care. The pediatric dental experience may be improved by the implementation of a therapy dog for anxiety, pain and behavior management. Our investigation will be the first to comprehensively assess physiological and psychological effects of AAT using a randomized controlled trial with a therapy dog intervention. If efficacious at anxiety, pain and behavior management, AAT will offer dental providers a non-invasive, low-risk approach to provide positive dental experiences, with the translational goal of reducing dental avoidance and its significant negative health sequelae.

EXPERIMENTAL DESIGN AND METHODS:

We have designed a cross-sectional prospective controlled trial assessing whether AAT (intervention with a therapy dog) impacts physiologic biometrics and perceptions of anxiety, pain and future expectations during a dental procedure in pediatric patients.

Screening for research participants includes searching the dental school graduate pediatric clinic schedule for potentially qualifying participants scheduled for operative or restorative dental treatment. Inclusion and exclusion criteria can be found in **Table 1**.

Table 1: Inclusion and Exclusion Criteria

Inclusion Criteria	Exclusion Criteria
Ages 7-17, male or female	Fear or allergy to dogs
Patient receiving treatment at UNC Pediatric Dental Clinic	Non-English and non-Spanish speakers
Parent and participant speak English or Spanish	Learning disability or a developmental delay
Able to comprehend and follow the requirement of the study	Medical history that complicates dental treatment
Frankl Behavioral Scale II, III, or IV	Xerostomia (dry-mouth)

This study has been approved by the UNC IRB (IRB Number: 19-1911; Title: Animal Assisted Therapy's Effects on Dental Patients)

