The research team calls to interview parents/caregivers of patients for enrollment criteria (**Table 1**). If a participant enrolls, he or she is assigned to a random weekday which determines the therapy animal's availability and will be either the active control group or the experimental AAT (dog intervention) group. The research team sets up a Go-Pro camera to film the visit and places the heart rate monitor (Shimmer or Polar device) on the patient's wrist in the pediatric clinic's consultation room. The participant is asked a standardized set of anxiety scale questionnaires: the Modified Child

Dental Anxiety Survey (MCDAS) and the Children's Fear Survey Schedule, Dental Subset (CFSS-SD). The child also rates their current pain level using Wong-Baker FACES (WBS), a numeric scale, and the visual analog scale (VAS). After the interview, the AAT intervention or control (i.e. coloring or sitting in silence) takes place for 3 minutes. The intervention group will interact with the therapy dog using a reproducible, standardized method. The handler will introduce the dog, and the participant pets the therapy dog, shakes her paw, gives her a treat, and then says goodbye in the clinic's consultation room. The control group will color a picture of a dog (active) or sit in silence (passive) for 3 minutes. C-DART database software will be used to record patient responses and guide the research visit in a structured manner. Following the intervention, the child is taken into the treatment room with the heart rate device still on his or her wrist, collecting objective physiological data. The GoPro camera will be taken into the treatment room, to provide for simultaneous video and physiological data collection. Salivary samples using salivettes will be collected at 4 timepoints during the visit, as described in **Table 1**. See **Figure 1** for treatment visit protocol.

[figure not shown]

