Figure 1: Overall Trial Design. Subject participation commences with consent and a pre-procedural survey. Subjects are randomized to a dog intervention or a control intervention (coloring or sitting in silence). The first baseline saliva sample S1 is collected, followed by the 2-minute therapy dog interaction for experimental participants (controls will sit in the room coloring for 2 minutes without a dog or sit in the room in silence). A second saliva sample S2 is collected 8 minutes later, after the intervention. The local anesthetic injection or insertion of handpiece will occur, followed by the third salivary sample S3 collected 8 minutes later to ensure sufficient time for variation in salivary biometrics. The dental procedure will continue and at the end of the visit participants will provide their last saliva sample S4 and fill out a post-procedure survey about their experience, perceived pain, anxiety and future expectations. Study participation concludes. Video (GoPro), skin galvanic response and heart rate data are continuously collected throughout the procedure. Salivary samples are processed for alpha-amylase and cortisol by the UNC Biobehavioral Lab (BBL).

Primary Aim: We will measure the physiologic effects of animal assisted therapy on pediatric patients' stress levels. Salivary alpha-amylase (sAA) functions as a digestive enzyme involved in the breakdown of glycogen and starch as well as part of the immune system by protecting the oral cavity from harmful microorganisms.³⁰ Salivary alpha-amylase increases in response to stress.³¹ In a study of 99 patients undergoing an invasive dental procedure, Jafari et. al presented evidence to support the dependability and objectivity of using sAA to measure the acute stress response in patients with dental anxiety.³²

Another physiological indicator of stress response that can be measured in the dental setting is salivary cortisol. The hypothalamic-pituitary-adrenal axis (HPA) is an important aspect of the endocrine system which leads to release of cortisol from the adrenal glands when the body is subject to physical or emotional stress.³³ As supported by the 2007 meta-analysis by Miller et. al exploring cortisol levels and stress, the use of salivary cortisol levels is well cited in the scientific literature to be a validated biomarker for stress.³⁴

To collect a saliva sample, the research team places a salivette in the mandibular vestibule for 5 minutes at the following timepoints:

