Table 2: Timepoints for salivary data collection

Timepoint	Description
S1	Baseline (pre-intervention, in consultation room)
S2	Post-intervention (8 minutes after intervention)
S3	8 minutes into the dental procedure
S4	8 minutes after completion of the procedure at the end of the study visit

Supplemental Aims: We will measure participants' heart rate throughout dental visit, will evaluate patients' perceptions of pain and anxiety using pre-, intra-, and post-procedural surveys and will analyze participants' behaviors using observational coding.

The Shimmer 3 GSR+ and Polar are small wearable wrist devices that measure heart rate through the wrist, with Shimmer 3 GSR+ also measuring sweat response through sensors that are fastened to the fingers. The Shimmer/Polar device will be connected to the patient during the pre-procedural interview, dog or control intervention, and procedure, continuously collecting heart rate and/or galvanic skin response (GSR) data.

Because heart rate is known to reliably increase under acute mental stress, it is widely used in medical research to evaluate stress response.³⁵ The Galvanic Skin Response (GSR) is a biomarker that quantifies the small electrical current induced by sweat which is released when the body is under stress.³⁶ The most significant psycho-activity and concentration of the epidermal sweat glands is on the sole of foot and the palm of the hand, particularly on the volar surface of the finger tips.³⁶ In a study completed by Caprara et. al in 2003, GSR was linked to increased dental anxiety in patients before undergoing a root canal treatment.³⁷

The video of the procedure as well as the heart rate data and GSR from the Shimmer device is loaded on to an external hard drive. The video will be coded with established behavioral codes using the Noldus software. The HR and GSR data are reviewed for inconsistencies using MindWare software. Both software are on a computer located in the bio-behavioral lab (BBL). The salivettes are transferred in a temperature-controlled container to the BBL where they are analyzed by ELISA for salivary alpha-amylase and salivary cortisol.

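### Both primary outcomes are measured in saliva, yet the plan neither standardises nor records recent eating or corticosteroid use, and the SAP adjusts for nothing: a cheap chance to reduce variance

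*Combined protocol and SAP*

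**What the plan says.** The Specific Aims section defines the primary aim as "analyzing objective physiologic measures (salivary amylase and cortisol) during invasive dental procedures". Table 1 lists the eligibility criteria. One concerns saliva, "Xerostomia (dry-mouth". The nearest other criterion is "Medical history that complicates dental treatment", which is tied to dental care and names no medicine.

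Under Experimental Design and Methods, screening is by telephone: "The research team calls to interview parents/caregivers of patients for enrollment criteria". No request about eating, drinking or medicines before the visit is described. For sampling, "the research team places a salivette in the mandibular vestibule for 5 minutes at the following timepoints", and Table 2 gives four timepoints, the first being "Baseline (pre-intervention, in consultation room". No condition on food, drink or clock time is attached to any of them.

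Under Primary Aim, the protocol says that amylase "functions as a digestive enzyme involved in the breakdown of glycogen and starch", and that the hormonal axis behind cortisol "leads to release of cortisol from the adrenal glands when the body is subject to physical or emotional stress".

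The Statistical Analysis Plan has one short paragraph. It names tests for ordinal and categorical survey items and a bivariate comparison by exposure to the dog, at the 0.05 level. It gives no method specific to the salivary outcomes, no covariate and no use of S1. It does not say whether levels or changes are compared.

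**The concern.** By excluding dry mouth, the plan accepts that a child's condition can spoil a saliva measurement, but it covers only that one condition. Its own descriptions make two further influences plausible: recent eating for a digestive enzyme, and corticosteroid medicine for an adrenal hormone. The medical-history exclusion may remove some children on corticosteroids, but only where the history complicates dental treatment.

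Precision is at stake. If these influences are present and unmeasured, the primary comparison carries variance unrelated to dental stress or to the dog. No sample size, power or SD is stated, so no known margin covers the loss. If the facts are not noted by S1, the analysis cannot separate them from stress afterwards.

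**Working it through.** **No planned figure to reproduce.** The documents give no sample size, effect size, SD or dropout rate. Every input below is an assumption, shown as a range.

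**1. Variance added by corticosteroid use, unadjusted cortisol levels.** Suppose a share p of children has cortisol lowered by a proportion f, and log cortisol otherwise has between-child standard deviation SD. Then

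variance inflation = 1 + p(1 − p)·[ln(1 − f)]² / SD², and effective sample lost = 1 − 1/inflation.

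| Case | p | f | SD | Inflation | Sample lost |
|---|---|---|---|---|---|
| Low end | 5% | 30% | 0.7 | 1 + 0.0475 × 0.127/0.49 = 1.01 | 1% |
| Central | 10% | 50% | 0.7 | 1 + 0.09 × 0.480/0.49 = 1.088 | 8% |
| Central | 10% | 50% | 0.5 | 1 + 0.09 × 0.480/0.25 = 1.173 | 15% |
| High end | 15% | 70% | 0.5 | 1 + 0.1275 × 1.450/0.25 = 1.74 | 43% |

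The high end needs all three extremes at once.

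**2. What this could mean for sample size.** For illustration, take a standardised difference of 0.5, two-sided alpha 0.05, 80% power and 1:1 allocation. The normal approximation gives 2 × (1.960 + 0.842)²/0.5² = 62.8, so 63 per arm. If a share g of the total outcome variance is avoidable noise, the required n is multiplied by 1/(1 − g).

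| g | n per arm for 80% power | Power if n stays at 63 |
|---|---|---|
| 0% | 63 | 80% |
| 5% | 67 | 78% |
| 10% | 70 | 76% |
| 20% | 79 | 71% |
| 30% | 90 | 65% |

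The central case in step 1 gives 62.8 × 1.088 = 68.3 to 62.8 × 1.173 = 73.7, so 69 to 74 per arm.

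**3. What S1 can remove.** If corticosteroid use lowers cortisol by the same proportion at S1 to S4, the shift ln(1 − f) is in every log value and cancels exactly in the log change from S1. The inflation in step 1 then falls to zero. Covariance adjustment with slope β leaves (1 − β)·ln(1 − f), so a corticosteroid covariate still has a use. More generally, adjusting for S1 leaves 1 − ρ² of the outcome variance: 91%, 75% or 51% for an assumed correlation of 0.3, 0.5 or 0.7. A food effect that changes during the visit, or a blunted cortisol response, would not be fully removed.

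**4. Should corticosteroid users be dropped from the cortisol analysis?** Keeping them leaves 1/inflation of the effective sample; dropping them leaves 1 − p. In the central case:

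- SD 0.7: keep 1/1.088 = 92%, drop 90%.
- SD 0.5: keep 1/1.173 = 85%, drop 90%.

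Keeping is better when (1 − p)²·[ln(1 − f)]²/SD² < 1. Over p = 5, 10, 15%, f = 30, 50, 70% and SD = 0.5, 0.7 (18 cells):

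- f = 30%: largest value 0.9025 × 0.127/0.25 = 0.46, so all six favour keeping.
- f = 50%, SD 0.7: largest value 0.9025 × 0.480/0.49 = 0.88, so all three favour keeping.
- f = 50%, SD 0.5: smallest value 0.7225 × 0.480/0.25 = 1.39, so all three favour dropping.
- f = 70%: smallest value 0.7225 × 1.450/0.49 = 2.14, so all six favour dropping.

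The split is 9 to 9. This assumes the same log-scale effect of the dog in corticosteroid users; a blunted response would favour dropping.

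**The case against.** The strongest reply is that every child supplies a sample before the intervention, so much of the supposed noise can be removed without any new data. This stands for the part that is constant across the visit (step 3), and it limits the 9% to 17% figure to unadjusted levels. It does not close the point, because the SAP does not plan that adjustment.

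A second reply is that the mechanism is only partly in the documents. Calling amylase a digestive enzyme does not say that a recent meal changes its measured concentration, in which direction or for how long. This also stands: the food effect is unquantified, and any interval before sampling must come from the assay laboratory.

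Third, the consent pages were removed from the text, and neither the telephone script nor the electronic visit form is reproduced. The claim must therefore be that the protocol and SAP text states no such instruction or record, not that none exists.

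A reader might go further and infer that a few children could dominate the cortisol result. A central variance rise of 9% to 17% does not support that. A reader might also infer bias between arms. Assignment is to a random weekday, and nothing in the documents links meals or medicines to the arm, so imbalance is possible but not shown. Finally, excluding corticosteroid users from the cortisol analysis may look like the natural remedy; step 4 shows that it loses precision about as often as it gains it.

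**Conclusion.** The gap in the text is real, and the point holds as a low-cost improvement, with low confidence. The plan neither standardises nor records two plausible influences on its primary outcomes, and its analysis adjusts for nothing, so avoidable variance may enter the primary comparison.

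The size cannot be derived from the documents. The range across the assumed inputs is a 1% to 74% rise in variance, and the low end is negligible. All of it concerns corticosteroid use and unadjusted cortisol levels; none of it measures food or amylase. The comparison between arms is not invalidated.

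**What to change.** **Protocol.** In the enrolment call, ask families in both arms alike for water only for a set interval before S1, the interval to be agreed with the assay laboratory. On the visit form, record before S1 the time of last food or drink, the clock time at S1 (so that the interval can be computed) and current corticosteroid use. Asking about corticosteroids already in the enrolment call would place that answer before the weekday is assigned.

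**SAP.** Analyse log cortisol and log amylase adjusted for S1. Keep all children in the primary analysis. Pre-specify corticosteroid use and recent eating as covariates. Leave corticosteroid users out of cortisol only as a sensitivity analysis.

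**Cost.** A few form fields, a short addition to the telephone script, a small scheduling request to families and a few SAP sentences. No child's medicines change. If enrolment has ended, only the S1 adjustment and a stated limitation remain feasible, plus the covariates where the facts happen to be on record elsewhere.

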Pre-intervention and post-intervention interviews will include the Child Fear Survey Schedule-Subset Dental (CFSS-SD), and the Modified Child Dental Anxiety Scale (MCDAS) to rate anxiety. To rate pain, the Wong-Baker FACES Scale (WBS), a numeric scale, and Visual Analog Scale (VAS) will also be used. The three pain rating scales will be repeated immediately after the injection. At the end of the procedures, the research team will repeat the CFSS-SD and the MCDAS for anxiety. They will also ask the child to rate his or her pain level again using the WBS, numeric scale, and VAS.

Pictorial representation of pain response, like The Wong-Baker FACES Scale (WBS), are preferred by children to express their level of pain regardless of age.³⁸ The Modified Child Dental Anxiety Survey (MCDAS) and the Children's Fear Survey Schedule, Dental Subset (CFSS-SD) are valid and reliable questionnaires in rating a child's anxiety in the dental setting.³⁹

STATISTICAL ANALYSIS PLAN:

To evaluate the values obtained on the various surveys, a RH Row Mean test will be utilized to compare questions that have Likert scale / ordinal responses and a chi square test will be used for categorical data. A bivariate analysis will be performed to compare the treatment outcome relative to the main exposure, which is the presence of the animal assisted therapy. The significance level will be $P < 0.05$.

Bibliography

1. Lima, D. S. M. *et al.* Does previous dental care experience make the child less anxious? An evaluation of anxiety and fear of pain. *Eur. Arch. Paediatr. Dent.* **22**, 139–143 (2021).
3. Coté, C. J. & Wilson, S. Guidelines for monitoring and management of pediatric patients before, during, and after sedation for diagnostic and therapeutic procedures. *Pediatr. Dent.* **41**, 259–260 (2019).
4. Marcus, D. A. *et al.* Animal-assisted therapy at an outpatient pain management clinic. *Pain Med.* **13**, 45–57 (2012).

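### The arm follows the visit weekday, but the SAP's tests have no visit-date term: if several study children share a date and same-day outcomes correlate, P values are too small

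*Combined protocol and SAP*

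**What the plan says.** Three parts of the combined document bear on this.

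- **Experimental Design and Methods.** An enrolled child is "assigned to a random weekday which determines the therapy animal's availability"; whether the child is a control or meets the dog follows from that day. Specific Aims mentions one dog: "the dental school has a certified therapy dog".
- **Figure 1 legend.** After consent and the pre-procedural survey, "Subjects are randomized to a dog intervention or a control intervention (coloring or sitting in silence". No unit, list, ratio or blocking is given.
- **Statistical Analysis Plan.** For surveys, "a RH Row Mean test will be utilized to compare questions that have Likert scale / ordinal responses", with chi-square for categorical data. Tests are judged at the 0.05 level. The treatment comparison is described in one sentence: "A bivariate analysis will be performed to compare the treatment outcome relative to the main exposure, which is the presence of the animal assisted therapy". No date, weekday, stratum, cluster or baseline term is named.

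The documents do not give the sample size, the number of study children per date, which weekdays are dog days, whether that map is fixed, or any ICC. They report no difference between dog days and other days.

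**The concern.** Drawing a weekday at random for each child is a form of randomization, and if the draw is kept it balances the children in expectation. It does not balance what happens on the day. If the day sets the arm, all study children on a date are in the same arm, and anything they share (staffing, delays, clinic mood, the dog's own day) falls wholly on one side of the comparison. Tests that treat children as independent then understate the standard error. The primary salivary comparison and every supplemental outcome rest on the same assignment.

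A second question is whether each weekday always belongs to one arm. If it does, part of any weekday effect is carried into the estimated dog effect, and enrolling more children does not remove it.

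A smaller point concerns timing. The methods text assigns the weekday at enrolment, before the questionnaires; the Figure 1 legend mentions randomization after the survey. Neither says when families learn the arm, and learning it early could affect the baseline anxiety answers and S1.

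**Working it through.** The plan has no design figure to reproduce; its only number here is the 0.05 level (taken as two-sided). Every other input below is an assumption, shown as a range.

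**1. Type I error of a child-level test.** With m children per date, the design effect is DE = 1 + (m − 1) × ICC, and the actual error is 2 × [1 − Φ(1.96/√DE)].

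| m | ICC | DE | 1.96/√DE | Type I error |
|---|---|---|---|---|
| 1 | any | 1.00 | 1.960 | 5.0% |
| 2 | 0.02 | 1.02 | 1.941 | 5.2% |
| 3 | 0.05 | 1.10 | 1.869 | 6.2% |
| 4 | 0.10 | 1.30 | 1.719 | 8.6% |

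With ICC 0 the result is 5.0% for any m.

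**2. Simulation checks, no treatment effect.**
- Row-mean-score test on a 5-level item (a stand-in for the named test), N = 40, 60 and 100: 5.3%, 5.2% and 5.1% at m = 2, ICC 0.02; 8.2%, 8.2% and 8.6% at m = 4, ICC 0.10.
- t-test on date means, same range: 4.6% to 5.4%.
- Unequal dates of 1 to 4 children, N = 40 or 100: the child-level test gives 5.4% to 7.7%; a date random-effect model with between-date degrees of freedom gives 3.5% to 5.0%, and 3.2% to 3.7% at ICC 0, so it is somewhat conservative.

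**3. Interval cost of allowing for date, equal dates.** Factor = √DE × t(.975, N/m − 2) / t(.975, N − 2).
- N = 100, m = 2, ICC 0.02: 1.010 × 1.013 = 1.02.
- N = 40, m = 4, ICC 0.10: 1.140 × 1.139 = 1.30.
- ICC 0: 1.013 to 1.139, from degrees of freedom alone.

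**4. Fixed weekday map.** The standard deviation of a weekday difference between arms, in outcome SDs, is √[ICC × (1/a + 1/b)] for a dog weekdays and b control weekdays. At weekday ICC 0.005 to 0.02 (assumed):
- 2 v 3 weekdays: √(0.005 × 0.833) = 0.065 to √(0.02 × 0.833) = 0.129.
- 1 v 4 weekdays: √(0.005 × 1.25) = 0.079 to √(0.02 × 1.25) = 0.158.

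These sizes apply only to the part of a weekday effect that is not already present at baseline.

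**5. What baseline can remove.** S1 and the first survey and pain scores are taken on the same day, before the intervention. Simulated at N = 60, m = 4, date ICC 0.10 and child-level correlation 0.6 (assumed), the unadjusted test rejects 8.0%. With a fully stable day effect, change scores reject 5.1% and baseline adjustment 5.7%. If the day effect correlates only 0.5 between the two times, they reject 8.8% and 8.3%, which is no help.

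**The case against.** The strongest reply is that the inflation needs facts the documents do not give.

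- **Children per date.** With one study child per date there is no date-level inflation, whatever the ICC. Visits are long and instrumented (four saliva samples, waits, filming, a wearable), so low daily numbers are plausible, though not stated. This stands, and the point is conditional on it. A reader might infer that correlated same-day outcomes are enough to make the P values wrong; the documents do not support that without more than one child per date.
- **The Figure 1 legend.** If it means allocation within the visit, both arms can occur on one date and the day effect no longer lies wholly between arms. This also stands. The methods text is the more specific account, and a random weekday draw is compatible with the legend's wording, but the order of events differs and the plan must settle it.
- **Same-day baselines.** A reader might infer that under a fixed map no analysis can separate weekday from dog. That goes too far: a weekday difference present at S1 and stable through the visit cancels in change from baseline. But the SAP does not specify a baseline adjustment, and one helps little if the day effect shifts during the visit.
- **Size.** The low end, 5.2%, is negligible, and all inputs are assumed. This is a reason for moderate weight. It does not justify leaving the SAP without a date term, because the visit date costs almost nothing to record.

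**Conclusion.** The point holds conditionally. If the methods text governs, two or more study children share a date and same-day outcomes correlate, the SAP's tests give error bars that are too narrow. Under the assumed 2 to 4 children per date and ICC 0.02 to 0.10, the true type I error is about 5.2% to 8.6%; with one child per date or ICC 0 it is 5.0%. The actual size cannot be found from the documents.

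If the weekday map is fixed, the estimate is the dog plus any weekday effect that arises or changes after baseline. Whether it is fixed is not stated. It would also be wrong to conclude that the trial is not randomized or that dog days are known to differ; the documents show neither. This should be fixed before analysis, with medium confidence.

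**What to change.** **(a) SAP wording.** *Outcomes will be compared by assigned arm, allowing for clustering by visit date. Continuous and score outcomes: a linear mixed model with the baseline value as covariate (S1 for saliva, the pre-intervention score for surveys), a random effect for visit date and Kenward-Roger degrees of freedom, or a t-test on date means. Categorical outcomes: a comparison of date-level proportions, or a permutation test that permutes arm by date, in place of the unadjusted chi-square test. If no date has more than one child, the date term is omitted.*

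**(b) Assignment.** State the unit of assignment and whether each weekday always belongs to one arm. If it does, limit the conclusion to the dog plus any post-baseline weekday effect; a date random effect does not cure this.

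**(c) Timing.** Reconcile the methods text with the Figure 1 legend, and do not tell families the arm before the baseline questionnaires and S1.

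**Cost.** SAP text and the visit date. Under the assumed inputs with N 40 to 100, intervals widen by about 2% to 30% before any gain from baseline adjustment; with unequal dates, by 7% to 17%. If ICC is really 0, 1% to 14% of width is spent for nothing. Simulated power at N = 60, 4 children per date and an effect of 0.8 SD, child-level test v date means, is 85% v 80% at ICC 0.02 and 83% v 70% at ICC 0.10. The 83% comes from a test with about 8.5% type I error, so that gap overstates the real loss.
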